2.2.13 Safety Analyses

All subjects enrolled in the study who received at least one dose of the medication will be included in the safety analysis (i.e. Safety Analysis Set).

2.2.13.1 Extent of Exposure

Treatment duration is defined as 8 weeks (Day 56 \pm 2 days). The date of the first and last doses of study medication will be collected from information recorded on the study drug admin page of the eCRFs. Study medication is to be orally taken once daily.

Extent of exposure to study medication will be tabulated by treatment group by 2 week intervals. The number of doses of study medication will be summarized by treatment group by each 2 week interval only for those subjects who returned to the clinic for each interval. The expected number of doses per 2 week intervals is 14, based on twice daily dosing. Compliance will be measured by calculating the number of doses/expected number of doses *100 and presented by treatment group for each interval.

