10.3 Dosage and Administration

This study involves a comparison of DS107 (2g and 1g) with placebo, administered orally once daily for a total duration of 8 weeks. **The last study drug administration should occur on the day preceding Week 8 (Visit 6) / Early Termination (ET) visit.** Patients will be randomized to one of the three treatment groups in a 1:1:1 ratio:

- Treatment group A: 1g DS107 (2 DS107 capsules and 2 placebo capsules) administered once-daily for 8 weeks
- Treatment group B: 2g DS107 (4 DS107 capsules) administered once-daily for 8 weeks
- Treatment group C: Placebo (4 placebo capsules) orally administered once-daily for 8 weeks

Patients will be required to administer the drug 2 hours after the consumption of food. Medication(s) for other conditions that are permitted in the study can be taken as usual.

Blister packs will consist of 7 rows of 4 capsules with each weekday detailed. Each row constitutes one dose. Patients will be instructed to take the 4 capsules **from left to right**, on the relevant day, as shown below:

To maintain the blind throughout the study, the DS107 capsules and placebo capsules will be identical in appearance.

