10.6 Drug Accountability

All IMPs supplies for this study must be retained in a safe place at all times of the study. Only personnel authorised by the principal investigator at each site should dispense the IMP and the accountability is the responsibility of the Investigator. The Investigator or pharmacist must complete the IMP supply form, verifying the receipt of IMP. The patients should return all used and unused packs of IMP to the study site at every visit. Following compliance assessment the packs of IMP will be retained in a secure location at the site until the end of the study. After the Clinical Research Associate (CRA) has completed a final drug accountability review the IMP may be returned or destroyed only when instructed by the CRA.

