2.2.5 Study Assessment Time Points

The study consists of seven protocol-specified visits which will be assessed as nominal visits from an analysis perspective:

- Visit 1/Screening visit (Day -30 to -1): Once informed consent has been obtained, the Investigator will assign a Patient Number and the subject will undergo the screening procedures. Following completion of a successful screening visit, patients will begin the comparative treatment period (8 weeks).
- Visit 2/Baseline (Day 0): At the start of the comparative treatment period, after confirmation of continued eligibility, patients will be randomly assigned to one of the three treatment regimens. Study medication is dispensed at Visit 2. The first dose of study medication will be carried out at the site once all baseline assessments have been completed. The patient will carry out their second dose of study medication in the evening of Day 0.
- Visits 3, 4 and 5: Follow-up visits at Week 2 (Day 14 ± 2 days), Week 4 (Day 28 ± 2 days) and Week 6 (Day 42 ± 2 days) respectively.
- Visit 6 – End of Treatment (EOT): Week 8 (Day 56 ± 2 days) for subjects who complete 8 weeks of treatment; earlier for subjects who discontinue treatment prematurely.
- Visit 7/Week 10: End of Study visit (Day 70 ± 3 days) for all subjects.
- Unscheduled Visits: Unscheduled visits may occur when a patient needs to make a visit in between the scheduled visit dates due to an AE, difficulty complying with the study protocol requirements, or a significant change in their disease state. All procedures that are medically necessary should be followed.

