2.2.13.3 Adverse Events

Counts and percentages of subjects who experienced any of the following will be presented by treatment group, as well as a total DS107 treatment group that includes both the 1g and 2g DS107 subjects: any AE, any IMP related AE, any AE requiring modification of study medication dosing (dose reduced, drug interrupted), discontinuations of study participation due to an AE (drug withdrawn), any serious adverse events (SAE), deaths, or IMP related SAEs. Only those adverse events determined to be treatment emergent (TEAE) will be presented (where Qlabel="Treatment

Emergent” from the SUPPAE SDTM dataset). Treatment emergent adverse events are those events with the date of AE onset being greater than or equal to the date of the first dose date of study drug. A two-sided Fisher Exact test will be utilized for an overall global test and for the pair-wise comparisons of each treatment compared to placebo.

Verbatim terms on the case report forms will be coded to preferred term (PT) and related system organ class (SOC) using MedDRA Coding Dictionary Version 19.1. The number and percentage of subjects who experience treatment-emergent adverse events (TEAE) will be tabulated by System Organ Class (SOC) and Preferred Term (PT) within each treatment group. The number of events will be tabulated by System Organ Class (SOC) and Preferred Term (PT) within each treatment group. In addition, a tabulation of adverse events that occur at a frequency of 2% or greater at the SOC or PT level will be prepared. A two-sided Fisher Exact test will be performed on system organ class (SOC) with a 2% or greater frequency to facilitate evaluation of potential safety differences among treatments.

Adverse events will be counted only once for a subject within each Preferred Term and System Organ Class; thus, since a subject may have more than one Preferred Term within an SOC, percentages of PT may not sum to the percentage in the SOC. If a subject reports a Preferred Term multiple times with differing severities (mild, moderate or severe), only the most severe is counted but all events will be counted. If a subject reports a Preferred Term multiple times with differing relationships to IMP, only the one that is related to IMP is counted.

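### Per-interval compliance is divided by a fixed 14 doses whatever the interval's actual length, and the SAP does not say how a partly taken row of capsules counts

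*SAP*

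**What the plan says.** SAP 2.2.13.1 (Extent of Exposure) summarises the number of doses in each 2-week interval, "only for those subjects who returned to the clinic for each interval". The compliance rule is: "Compliance will be measured by calculating the number of doses/expected number of doses *100 and presented by treatment group for each interval". The denominator is fixed: "The expected number of doses per 2 week intervals is 14, based on twice daily dosing". The same section also says: "Study medication is to be orally taken once daily". It makes no adjustment for actual visit dates, does not define a dose, and has no rule for a dose taken only in part.

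SAP 2.2.5 sets the visit windows: "Follow-up visits at Week 2 (Day 14 ± 2 days), Week 4 (Day 28 ± 2 days) and Week 6 (Day 42 ± 2 days) respectively". Week 8 is Day 56 with the same 2-day allowance. That section also describes a second dose on the evening of Day 0.

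Protocol 10.3 gives each day's medication as a blister row of four capsules: "Each row constitutes one dose". Group A's row holds two active and two placebo capsules, group B's four active and group C's four placebo. Protocol 10.1 gives 500 mg DGLA per active capsule.

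On data sources, Protocol 10.6 says: "The patients should return all used and unused packs of IMP to the study site at every visit". Protocol 8.2.2 has the patient log every administration. SAP 2.2.3 plans a listing of study medication use, SAP 2.2.13.3 counts patients with "any AE requiring modification of study medication dosing (dose reduced, drug interrupted"), and SAP 2.2.13.3.3 plans a listing of patients whose dosing changed.

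**The concern.** Two parts of the compliance ratio look unsound. The denominator assumes that every interval lasts exactly 14 days, which the plan's own visit windows do not require. A patient who takes everything can then look non-compliant or over-dosed, and a patient who misses doses in a long interval can look fully compliant.

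The numerator is undefined for partial rows. This matters more here than in most trials, because the arms differ only in how many of the four capsules are active. The number of capsules swallowed therefore determines the dose received. Protocol section 3 presents the study as dose-finding. The most common adverse events reported with DS107 capsules were gastrointestinal (Protocol 1.6), which makes skipped capsules plausible, although the documents report none. If skipping were concentrated in the 2 g arm, the doses received in the two active arms would move closer together. A compliance summary blind to partial rows would not warn the reader before a flat dose-response was interpreted. Plasma DGLA, the natural cross-check, is left to a separate document (SAP 2.2.12.3).

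**Working it through.** **1. Reproduce the plan's 14.** Expected doses = days × doses per day. 14 × 1 = 14, which matches. 14 × 2 = 28, which does not. The figure agrees with the once-daily sentence in SAP 2.2.13.1 and not with the twice-daily basis attached to it. Against 28, a patient taking 14 doses would score 14/28 = 50%. A second Day 0 dose would give 15/14 = 107.1% in a 14-day first interval. These statements must be reconciled. The steps below use once-daily dosing because only that reproduces 14.

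**2. Permitted interval lengths.** Baseline is Day 0. The windows are Day 12–16, 26–30, 40–44 and 54–58. The shortest interval is the earliest current visit minus the latest previous visit; the longest is the latest current visit minus the earliest previous visit.

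| Interval | Shortest | Longest |
|---|---|---|
| Baseline to Week 2 | 12 − 0 = 12 days | 16 − 0 = 16 days |
| Week 2 to Week 4 | 26 − 16 = 10 days | 30 − 12 = 18 days |
| Week 4 to Week 6 | 40 − 30 = 10 days | 44 − 26 = 18 days |
| Week 6 to Week 8 | 54 − 44 = 10 days | 58 − 40 = 18 days |

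**3. Score of a patient who misses nothing.** Compliance = 100 × days / 14.

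- First interval: 12/14 = 85.7% to 16/14 = 114.3%.
- Later three: 10/14 = 71.4% to 18/14 = 128.6%.
- Values above 100% require enough capsules in hand; the documents do not state how many packs are dispensed per visit.

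**4. Non-adherence hidden or exaggerated.**

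- 14 doses in 18 days: true adherence 14/18 = 77.8%, reported 14/14 = 100%.
- 80% true adherence over 18 days: 0.8 × 18 / 14 = 102.9%.
- 80% true adherence over 10 days: 0.8 × 10 / 14 = 57.1%.

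**5. Whole course.** The first dose follows the Day 0 visit and the last falls the day before Visit 6 (Protocol 8.2.3 and 8.2.7), giving 54 to 58 dosing days against 4 × 14 = 56. 54/56 = 96.4% and 58/56 = 103.6%. A long interval tends to be offset by a short one.

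**6. Partial rows.** Take a group B patient who swallows two of four capsules daily for 14 days. The amount received is 2 × 500 = 1,000 mg a day, group A's assigned total. By capsules, 28/56 = 50%. Under the SAP the score depends on an unstated convention:

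- half row counts as 0: 0/14 = 0%;
- half row counts as 0.5: 7/14 = 50%;
- any occasion counts as 1: 14/14 = 100%.

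**7. With a corrected ratio.** If the denominator is 4 × actual dosing days, a fully adherent patient scores 100% in every interval, and the patient in step 6 scores 50%.

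**The case against.** **The 14 may be right.** The SAP speaks of 2-week intervals and never says that they run visit to visit. For calendar blocks of 14 days at one dose a day, 14 is correct. This stands as a possibility, but limiting the summary to patients who came back for each interval, and collecting packs and logs visit by visit, points to visit-based intervals. If calendar blocks are meant, the SAP should say so.

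**The ranges are extremes.** Reaching 10 or 18 days needs consecutive visits at opposite edges of their windows, and it cannot happen in the first interval. A reader might infer that intervals will really run 10 to 18 days; the documents show only that they may. Nothing suggests that visit timing would differ by arm under blinding, so the between-arm comparison is little affected by the denominator. Both points stand.

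**The SAP does not say that it counts occasions.** A reader might infer that a half row automatically scores 100%. The protocol makes a full row one dose, so a half row could as well score zero. The gap is an undefined numerator, and 100% is only one of its possible consequences.

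**Other outputs exist.** A reader might infer that nothing planned could reveal a 2 g patient taking 1 g. That goes too far: the count of dose-modifying adverse events, the dosing-change listing and the medication-use listing may reveal some such patients. They may miss capsule-skipping that is never reported as an event or a dose change, and none of them is specified to give dose received by arm.

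**Downstream harm is not shown.** A reader might infer that adherent patients would be lost from the per-protocol set. Neither document states a compliance cut-off or ties this percentage to that set, which is settled by blinded review and is supportive only.

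**Conclusion.** The point holds as a minor but genuine defect in a descriptive analysis. Applied visit to visit, the stated rule can score a fully adherent patient 86% to 114% in the first interval and 71% to 129% in each later one at the permitted extremes. It can also report 100% for 77.8% adherence. The whole-course error is small, 96.4% to 103.6%, but the SAP specifies reporting by interval, where the error is largest. This rests on visit-to-visit intervals and once-daily dosing; the upper readings also assume sufficient supply.

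Separately, the undefined numerator leaves a half-row taker in the 2 g arm at 0%, 50% or 100%. The highest value applies only if any dosing occasion counts as a dose.

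The consequence is for exposure reporting and for reading the dose-response. The primary analysis uses the full analysis set as randomised and does not use compliance.

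**What to change.** In SAP 2.2.13.1, define compliance as capsules taken / (4 × actual dosing days in the interval) × 100, and report it by arm for each interval and for the whole course. Take the days from dose and visit dates, and the capsules from returned packs or the compliance log. Define dosing days as days on which a dose was due, so that missed days stay in the denominator. State to which interval a visit-day dose belongs, and how days after stopping study drug are handled for patients who keep attending (Protocol 7.5.2). State also whether intervals are visit-based.

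Reconcile the twice-daily basis in SAP 2.2.13.1 and the second Day 0 dose in SAP 2.2.5 with the once-daily text. The factor of 4 rests on the once-daily text. Correcting only the frequency wording would leave both defects above in place.

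The cost is SAP wording and simple programming. Protocol 10.6 mentions a compliance assessment of returned packs but not that capsules are counted and entered, so one eCRF field may be needed. A grams-per-day summary is not part of this fix: for group A it would need to be known which capsules in a partial row were active, and the documents do not show that this is recorded.

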2.2.13.2 Safety Endpoint(s)

The safety objective is to compare the safety of orally administered DS107 capsules (1g & 2g) versus placebo, in the treatment of adult patients with moderate to severe AD. Results will be pooled for 1g and 2g treatment groups as well.

2.2.13.3 Adverse Events

Counts and percentages of subjects who experienced any of the following will be presented by treatment group, as well as a total DS107 treatment group that includes both the 1g and 2g DS107 subjects: any AE, any IMP related AE, any AE requiring modification of study medication dosing (dose reduced, drug interrupted), discontinuations of study participation due to an AE (drug withdrawn), any serious adverse events (SAE), deaths, or IMP related SAEs. Only those adverse events determined to be treatment emergent (TEAE) will be presented (where Qlabel="Treatment

Emergent” from the SUPPAE SDTM dataset). Treatment emergent adverse events are those events with the date of AE onset being greater than or equal to the date of the first dose date of study drug. A two-sided Fisher Exact test will be utilized for an overall global test and for the pair-wise comparisons of each treatment compared to placebo.

Verbatim terms on the case report forms will be coded to preferred term (PT) and related system organ class (SOC) using MedDRA Coding Dictionary Version 19.1. The number and percentage of subjects who experience treatment-emergent adverse events (TEAE) will be tabulated by System Organ Class (SOC) and Preferred Term (PT) within each treatment group. The number of events will be tabulated by System Organ Class (SOC) and Preferred Term (PT) within each treatment group. In addition, a tabulation of adverse events that occur at a frequency of 2% or greater at the SOC or PT level will be prepared. A two-sided Fisher Exact test will be performed on system organ class (SOC) with a 2% or greater frequency to facilitate evaluation of potential safety differences among treatments.

Adverse events will be counted only once for a subject within each Preferred Term and System Organ Class; thus, since a subject may have more than one Preferred Term within an SOC, percentages of PT may not sum to the percentage in the SOC. If a subject reports a Preferred Term multiple times with differing severities (mild, moderate or severe), only the most severe is counted but all events will be counted. If a subject reports a Preferred Term multiple times with differing relationships to IMP, only the one that is related to IMP is counted.

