7.2 Inclusion Criteria

1. Patients with a clinically confirmed diagnosis of active AD according to Hanifin and Rajka criteria.
2. Patients with moderate to severe AD at baseline as defined by an IGA of minimum 3 at baseline.
3. Patients with an EASI score of ≥ 12 at screening and baseline.
4. Patients with AD covering a minimum 10% of the body surface area at baseline.
5. Patients whose pre-study clinical laboratory findings do not interfere with their participation in the study, in the opinion of the investigator.
6. Patients who are able and willing to stop all current treatments for AD throughout the study (except for allowed emollients).
7. Patients who are on a stable dose of a bland emollient applied BD (twice daily) for at least 7 days prior to baseline.
8. Male or female patients who are aged 18 years and older on the day of signing the informed consent form (ICF).
9. Female patients and male patients with female partners of child bearing potential must use adequate contraception or have a sterilized partner for the duration of the study. Adequate contraception is defined as: systemic hormonal contraceptives, intrauterine device or barrier method of contraception in conjunction with spermicide, or agree to sexual abstinence. Hormonal contraceptives must be on a stable dose for at least one month before baseline.
10. Patients who are able to communicate well with the investigator, to understand and comply with the requirements of the study, and understand and sign the written Informed Consent.

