9.2.2 Physical Examination

A physical examination will be performed by the investigator as per the Study Flow Chart (Appendix 1) at every visit in accordance with local practices. This examination will be symptom-directed, i.e., a standard panel of body systems will not be assessed unless indicated by patient. For example should the patient report to the investigator the presence of ‘rash’ then

the skin would be evaluated. It is not required that additional body systems are assessed unless clinically warranted. Any clinically significant abnormal results should be recorded in the CRF. Changes in findings of the physical examination compared with the baseline examination should be recorded as an AE.

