11 ADVERSE EVENTS AND SERIOUS ADVERSE EVENTS

11.1 Definitions of Adverse Events

11.1.1 Seriousness

Adverse Events (AE):

Any undesirable experience occurring to a patient that has signed the ICF and who has taken their first dose of the study drug, whether or not considered related to the investigational IMP(s). All AEs must be recorded in the case report form, defining relationship to IMP and severity. AEs should also be recorded by the Investigator in the patient file/notes.

Serious Adverse Events (SAE):

If a patient experiences a serious adverse event after the first dose of the study drug, the event will be recorded as a serious adverse event.

A serious adverse event (experience) or reaction is any untoward medical occurrence that at any dose:

- results in death
- is life-threatening
- requires in-patient hospitalization or prolongation of existing hospitalization
- results in persistent or significant disability/incapacity, or
- is a congenital anomaly/birth defect

Note: The term "life-threatening" in the definition of "serious" refers to an event in which the patient was at risk of death at the time of the event. It does not refer to an event which hypothetically might have caused death if it were more severe.

Medical and scientific judgment should be exercised in deciding whether expedited reporting is appropriate in other situations, such as important medical events that may not be immediately life-threatening or result in death or hospitalization but may jeopardize the patient or may require intervention to prevent one of the other outcomes listed in the definition above. These should also usually be considered serious.

Examples of such events are intensive treatment in an emergency room or at home for allergic bronchospasm, blood dyscrasias or convulsions that do not result in hospitalization, or development of drug dependency or drug abuse.

Unexpected Adverse Event (UAE):

An experience not previously reported in the Investigator's Brochure or similar product information sheet such as the Summary of Products Characteristics (SPC).

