11.3 Differentiation of Treatment Failure and AE

Please note, that the lack of improvement of the symptoms of AD is not an AE and should be reported as treatment failure.

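### AD worsening may be recorded as an AE, and the SAP tests any AE and the skin SOC with no supplementary count that leaves it out

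*SAP*

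**What the plan says.** Three Protocol sections bear on whether worsening of AD is an adverse event.

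- Section 11.1.1 defines an AE as "Any undesirable experience occurring to a patient that has signed the ICF and who has taken their first dose of the study drug". The event need not be thought related to the product.
- Section 9.2.2 adds "Changes in findings of the physical examination compared with the baseline examination should be recorded as an AE".
- Section 11.3 makes the only exception: "the lack of improvement of the symptoms of AD is not an AE and should be reported as treatment failure". It does not mention worsening or flare.

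Section 7.2 admits "Patients who are able and willing to stop all current treatments for AD throughout the study (except for allowed emollients"), so background control of the disease is limited.

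SAP 2.2.13.3 takes all treatment-emergent AEs. The summary categories begin "any AE, any IMP related AE, any AE requiring modification of study medication dosing (dose reduced, drug interrupted") and go on to discontinuations, SAEs and deaths. On testing it says "A two-sided Fisher Exact test will be utilized for an overall global test and for the pair-wise comparisons of each treatment compared to placebo", and further "A two-sided Fisher Exact test will be performed on system organ class (SOC) with a 2% or greater frequency". TEAEs "will be tabulated by System Organ Class (SOC) and Preferred Term (PT) within each treatment group". No category, exclusion or sensitivity analysis sets AD worsening apart.

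**The concern.** A flare after the first dose is an undesirable experience and can show as a change on skin examination. It is not mere lack of improvement. On the ordinary reading of the three sections it can therefore enter the AE data.

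Patients have at least moderate disease and use only emollients, so flares are plausible in every arm. If DS107 is effective they should be more frequent on placebo. The any-AE row, and the SOC in which AD terms are coded, would then combine a failure-of-efficacy event that favours DS107 with any drug harm that goes the other way. SAP 2.2.13.2 states the safety objective as a comparison with placebo. Similar any-AE rates could be read as good tolerability when part of the similarity comes from flares.

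**Working it through.** **The plan's own figure.** The documents give no figure for the AE comparisons. Protocol 12.3 gives 100 per arm and 45% power for response rates of 21.6% and 11.8%, two-sided 5%. Normal approximation: the difference is 0.098 and the mean rate 0.167. The null SE is √(2×0.167×0.833/100) = 0.0527 and the alternative SE √((0.118×0.882 + 0.216×0.784)/100) = 0.0523. Power = Φ((0.098 − 1.96×0.0527)/0.0523) = 45.9%, which agrees. This only fixes n and alpha for what follows.

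**Inputs.** n = 100 per arm and two-sided 0.05 come from the Protocol, and the Fisher test from the SAP. All AE and flare rates below are assumptions. Write h for the rate of other AEs and w for AD worsening, with 0 for placebo and 1 for DS107, and assume that the two event types are independent within an arm.

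**Formula.** P(any) = 1 − (1 − h)(1 − w). The difference between arms splits into two parts:

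P1 − P0 = (1 − w0)(h1 − h0) − (1 − h1)(w0 − w1).

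The first term is the true excess after dilution by background flares. The second is the offset from fewer flares on DS107. Power is by full enumeration of the two binomials.

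**Any AE, other AEs 20% placebo v 35% DS107 (excess 15 points, power 61%)**

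| Worsening, placebo v DS107 | Any AE, placebo v DS107 | Difference (points) | Power |
|---|---|---|---|
| 10% v 10% | 28% v 41.5% | 13.5 | 46% |
| 20% v 20% | 36% v 48% | 12.0 | 36% |
| 10% v 5% | 28% v 38.25% | 13.5 − 3.25 = 10.25 | 28% |
| 20% v 15% | 36% v 44.75% | 12.0 − 3.25 = 8.75 | 20% |
| 20% v 10% | 36% v 41.5% | 12.0 − 6.5 = 5.5 | 10% |
| 30% v 15% | 44% v 44.75% | 10.5 − 9.75 = 0.75 | 4% |

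In the 20% v 10% row, dilution alone takes power from 61% to 36%, and the offset takes it from 36% to 10%.

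**Skin SOC, other skin AEs 3% placebo v 13% DS107 (excess 10 points, power 69%)**

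| Worsening, placebo v DS107 | Skin SOC, placebo v DS107 | Difference (points) | Power |
|---|---|---|---|
| 10% v 10% | 12.7% v 21.7% | 9.0 | 33% |
| 10% v 5% | 12.7% v 17.35% | 9.0 − 4.35 = 4.65 | 11% |
| 15% v 5% | 17.55% v 17.35% | 8.5 − 8.7 = −0.2 | 3% |

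The offset is nearly complete only when the placebo excess of flares is about as large as the harm. With a smaller efficacy effect it is partial.

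**The case against.** The case against is substantial, and most of it stands.

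- **The premise is an inference.** The unscheduled-visit text (Protocol 8.2.1 and 8.2.2, SAP 2.2.5) lists an AE and a significant change in disease state as separate reasons for a visit. The examination in Protocol 9.2.2 is symptom-directed, and AD severity has its own instruments. A reader might infer that every flare will be counted as an AE. The documents support only that it may be, and perhaps differently by site.
- **Two rows are largely protected.** Protocol 7.5.2 lists lack of efficacy apart from unacceptable AEs as a reason for stopping product, and SAP 2.2.2 tabulates reasons for discontinuation by arm. Protocol 11.1.3 classes an event as not related when another cause can explain it, which would fit many flares. The AE-discontinuation and IMP-related rows are therefore only partly exposed.
- **The known signal is not hidden.** Protocol 1.6 reports mainly gastrointestinal AEs with the capsules. That SOC is tested separately if it reaches 2%, and AD terms coded to skin cannot reach it.
- **AD terms are already visible** by arm in the preferred-term tables.
- **The rates are assumed, and much of the power loss is plain dilution**, as the equal-worsening rows show.
- **No safety decision rule hangs on these p-values.** The SAP describes the SOC tests as an aid to evaluation.

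One gap remains. The preferred-term tables cannot be de-duplicated by subject. SAP 2.2.13.3 itself notes that preferred-term percentages may not add up to the SOC percentage. A reader cannot derive from them how many subjects had any AE, or any skin AE, other than AD worsening.

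**Conclusion.** The point holds for two comparisons: any AE, and the SOC in which AD terms are coded. That this is the skin SOC is usual coding practice and is not stated in the documents. In these comparisons AD worsening can partly offset and dilute an excess of other AEs.

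In the scenarios above, a 15-point any-AE excess shrinks to between 13.5 and 0.75 points, and power falls from 61% to between 46% and 4%. These figures rest on assumed rates, on independence of the two event types, and on sites recording worsening as an AE. The documents fix none of these.

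A reader might go further and conclude that the whole safety comparison is masked. The documents do not support that: the gastrointestinal test, the preferred-term tables, the relatedness definition and the separate lack-of-efficacy category all limit the effect. Nor do they support replacing the all-TEAE comparison with one that excludes AD worsening, because that would drop any worsening caused by the product itself.

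**What to change.** In SAP 2.2.13.3, keep the all-TEAE analysis as it is. Add a supplementary comparison with the same Fisher test for two counts, any TEAE and the skin SOC, each excluding subjects whose only qualifying events are on a list of AD-worsening preferred terms. Fix that list before unblinding. Present the result beside the all-TEAE result and the preferred-term line for AD worsening, as an aid to reading them and not as a replacement.

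In Protocol 11.3, add a sentence on how worsening, as distinct from lack of improvement, is to be recorded, so that all sites do it the same way.

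The cost is one term list, a few extra table rows and one clarifying sentence.
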